#### 2.1.2 Exclusion Criteria

- 2.1.2.1 Documented hypersensitivity to clobetasol.
- 2.1.2.2 Use of clobetasol ointment intra-orally at any time during the last 6 weeks period.
- 2.1.2.3 Pregnant or breast-feeding females due to possible toxicity to the fetus or infant.
- 2.1.2.4 Inability to understand the investigational nature of the study to provide informed consent.
- 2.1.2.5 Patients who, for medical or other reasons, are unable to comply with the study procedures.

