## 1.2.3 cGVHD Therapy

## 1.2.3.1 Systemic and topical corticosteroids

The treatment for cGVHD consists of various systemic immunosuppressive agents, most commonly systemic corticosteroids, cyclosporine, tacrolimus, mycophenolate, sirolimus and phototherapy. Long-term immunosuppressive treatment for GVHD has a variety of serious complications including life-threatening infections, aseptic bone necrosis, hypertension, and secondary diabetes.

Corticosteroids are the most commonly used systemic treatment of both acute and chronic GVHD. Immunosuppressive and anti-inflammatory effects of corticosteroids are mediated through multiple mechanisms including immune cell apoptosis and interference with dendritic cell maturation. The critical role of dendritic cells in the development of GVHD has been outlined in several studies. One study demonstrated the potential of GVHD prevention via depletion of host antigen presenting cells in a murine model.. In another animal study, local depletion of Langerhans cells in skin prevented GVHD. Corticosteroids have been shown to prevent development of dermal dendritic cells *in vitro*.. Additionally, topical corticosteroids induced apoptosis in the murine epidermal Langerhans cells and CD8+T cells.

Topical corticosteroids such as dexamethasone 0.01% oral rinse and clobetasol 0.05% ointment are used widely for treatment of oral cGVHD, although their efficacy has not been formally evaluated in this condition. Ointments and creams have a disadvantage of uneven and cumbersome application, furthermore, it is difficult to estimate the systemic versus local effect. Unlike solutions used as rinses, ointments can be easily swallowed and absorbed through the gastrointestinal tract. At the NIH Clinical Center, both dexamethasone oral rinse and clobetasol ointment have been used with variable success. In general, complicated application procedures reduce compliance and make evaluation of response difficult. Oral rinses have a particular advantage when a significant oral cavity area is affected as the contact with the entire surface is ensured with potential decrease in systemic absorption.

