## 2 ELIGIBILITY ASSESSMENT AND ENROLLMENT

## 2.1 ELIGIBILITY CRITERIA

## 2.1.1 Inclusion Criteria

- 2.1.1.1 Age: 12 years 99 years.
- 2.1.1.2 Diagnosis: clinically significant oral cGVHD after allogeneic HSCT with severity score of at least 2 on erythema subset and/or at least 1 on ulceration subset and a composite

score  $\geq$ 20 of the Oral Mucositis Rating Scale (OMRS) scale (**Appendix A**) confirmed by the principal investigator (PI), clinical study chair (CSC), or lead associate investigator (LAI).

- 2.1.1.3 Hematologic Function: Patients must have a platelet count  $\geq 20,000/\mu L$  at the time of the initial evaluation.
- 2.1.1.4 Informed Consent: All patients or their legal representative (for patients <18 years old) must sign an IRB approved informed consent document (cGVHD natural history protocol 04-C-0281 or any NCI protocol allowing for screening procedures) prior to performing studies to determine patient eligibility. After confirmation of patient eligibility all patients or their legal representative must sign the protocol specific informed consent. For pediatric patients age appropriate assent will be obtained in accordance with NIH guidelines.
- 2.1.1.5 Patients must be able to rinse and expectorate study medication rather than swallow it. Female patients must be willing to practice birth control (including abstinence) during and for two months after treatment, if of childbearing potential.
- 2.1.1.6 Patients must have the ability and willingness to come to Clinical Center for bi-weekly follow-up appointments.
- 2.1.1.7 No change in systemic immunosuppressive therapy (type or intensity level) within 2 weeks prior to enrollment.
- 2.1.1.8 A 7-day washout period is required if patients are currently using another oral topical treatment for mouth lesions. Patients currently using clobetasol oral topical treatment are not eligible for this study.

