The primary endpoint is the fraction of subjects who experience a 25% improvement in their OMRS compared to their own baseline. The fraction will be estimated with a two-tailed 95% confidence interval as the primary outcome. This will be done using all 34 patients together provided that the changes from baseline to day 28 for the two groups are sufficiently similar. A formal test will be performed assess their comparability. This will be determined conservatively, by obtaining the actual difference in the individual OMRS for each patient at baseline (day 0 for initial clobetasol and day 14 for those initially given placebo) vs. the value after day 28 of clobetasol and comparing those differences between the two randomized groups using a two-tailed Wilcoxon rank sum test. If the p-value for that comparison is >0.30, then the two groups will be considered sufficiently similar to allow pooling of the results and to report a combined

fraction of patients who have a 'response' to 28 days of clobetasol. In this case 34 patients will be sufficient to allow the proportion of patients with a response of 75% or more to have a two-sided 95% confidence interval of +/- 15% or less, which will be considered sufficiently precise. Fractions of responses <75% would have slightly wider confidence interval widths.

An important secondary endpoint is to compare the changes from day 0 in the OMRS until day 14 between those who only receive placebo by that point vs. those who received clobetasol. This evaluation will be done both with respect to the fraction with a response by 2 weeks, as well as comparing the actual changes in OMRS from day 0 to day 14.

By enrolling 17 patients per arm, a 0.10 alpha level one-tailed Fisher's exact test will have 80% power to detect a difference between a potential 75% of patients having a 25% or greater decrease in severity score on the clobetasol arm and about half that amount, 35%, on the placebo arm. A one-tailed test is sufficient for this secondary objective in this study since we will not expect clobetasol to be associated with a lower fraction of patients with benefit compared to placebo and because this is intended to be a pilot study to determine if a potential trend of magnitudes anticipated, but not necessarily a statistically significant gain, may be detected. Should very promising results be obtained, then a subsequent trial could be conducted to build upon and further confirm the benefit noted.

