## **11 HUMAN SUBJECTS PROTECTIONS**

## 11.1 RATIONALE FOR SUBJECT SELECTION

No subjects will be excluded from participation based on sex, race or ethnicity. The study will be open to all subjects who satisfy the inclusion criteria and provide an informed consent to the protocol. From previous transplant protocol recruitment patterns at NIH we expect that over 80% of patients in this study will be adults over 18.

Recruitment: Subjects will be primarily recruited from NIH Clinical Center hematopoietic stem cell transplant clinics but could be referred from the outside institutions.

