## **Patient Enrollment**

## **Recipient**

- Date of birth, age, sex, race, ethnicity
- Height
- Weight
- Karnofsky Performance Status
- Date of original diagnosis of the underlying disease (month/year)
- Diagnosis for which transplant was performed
- Date and type of transplant
- Conditioning regimen
- Acute GVHD yes/no
- Chronic GVHD date of diagnosis
- Chronic GVHD classification (late, overlap, classic)
- Prior systemic therapy for cGVHD
- Prior oral therapy for cGVHD
- Date of Informed Consent signature, consent version and date of registration
- Optional Baseline History/Physical
- Baseline Symptoms
- Intensity of current immunosuppression: None, Mild (single agent prednisone ≤0.5 mg/kg/day), Moderate (prednisone ≥0.5 mg/kg/day and or any single agent/modality), High (2 or more agents/modalities ±prednisone ≥0.5 mg/kg/day)
- Clinician's impression of activity: Inactive, off systemic therapy or topical immunosuppression; Inactive, on systemic therapy or topical immunosuppression; Active, irrespective of the level of current therapy; Highly Active, irrespective of the level of current therapy
- Findings of consultations done at screening

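### The 6-week look-back for prior intra-oral clobetasol covers only the ointment, so a patient who recently stopped another form can enter with little or no washout from the study drug

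*Combined protocol and SAP*

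**What the plan says.** Three eligibility rules bear on earlier topical treatment of the mouth.

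- Exclusion 2.1.2.2: "Use of clobetasol ointment intra-orally at any time during the last 6 weeks period". This is the only rule with a 6-week window, and it names only the ointment.
- Inclusion 2.1.1.8, on clobetasol: "Patients currently using clobetasol oral topical treatment are not eligible for this study". This covers any oral topical form, but only while it is in use.
- Inclusion 2.1.1.8, on other topicals: "A 7-day washout period is required if patients are currently using another oral topical treatment for mouth lesions". Section 3.3.1 repeats this washout and does not mention clobetasol there.

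The data elements in Appendix H include "Prior oral therapy for cGVHD", but that is an item to record, not a condition of entry. Section 1.2.3.1 says that at the site "both dexamethasone oral rinse and clobetasol ointment have been used with variable success". Section 11.1 adds that patients, although recruited mainly from the site's own transplant clinics, "could be referred from the outside institutions".

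**The concern.** The exposure is the same drug at the same site in the mouth, yet the rule differs by vehicle. If a 6-week gap is wanted after ointment, the protocol gives no reason why a patient who stopped a cream, gel or solution should need less.

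Two sets of measurements could be affected. The first is the OMRS baseline. Under section 10.2 the primary estimate is the fraction of patients whose OMRS improves by 25% against their own baseline, pooled over 34 patients if the two groups look similar. This is a within-patient change and not a contrast between arms, so randomisation does not protect it from a baseline still influenced by earlier clobetasol. The second is the set of reference values for systemic exposure: the pre-treatment cortisol, ACTH level and ACTH stimulation test in section 3.3.1, and the baseline plasma clobetasol level in section 5.1.3. Recent use of the study drug could leave these short of a drug-free baseline.

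**Working it through.** The plan states no figure on this point, so the main check sets the rules side by side. Enrolment is taken as day 0, which is an assumption.

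**Minimum gap between the last intra-oral clobetasol and day 0**

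| History | Rule that applies | Minimum gap |
|---|---|---|
| Ointment, stopped | 2.1.2.2 | 6 × 7 = 42 days |
| Any form, still in use | 2.1.1.8, current use | not eligible |
| Cream, gel or solution, stopped; generous reading | 7-day washout in 2.1.1.8 | 7 days |
| Cream, gel or solution, stopped; literal reading | none | 0 days |

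The literal reading gives 0 because the washout is written for someone now using a different topical treatment. A patient who has already stopped clobetasol fits neither half of 2.1.1.8. The shortfall against the ointment rule is 42 − 7 = 35 days on the generous reading and 42 − 0 = 42 days on the literal one. Nothing in sections 2.1, 3.3.1 or Appendix H closes it.

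**Gap to the primary baseline, by arm.** Sections 3.1 and 10.2 set the OMRS baseline at day 0 for the clobetasol-first group and day 14 for the placebo-first group. For a recent stopper of a non-ointment form, the minimum gap to that baseline is then:

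- clobetasol-first: 0 to 7 days;
- placebo-first: 0 + 14 = 14 to 7 + 14 = 21 days.

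Any residual effect would therefore enter the two groups unequally. It would also enter the rank sum test (p > 0.30) that decides whether they are pooled.

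**Upper bound on the effect.** One patient is 1/34 = 2.9 points of the pooled fraction, or 1/17 = 5.9 points of one arm's fraction (section 10.2: "By enrolling 17 patients per arm"). That is the weight of any patient, and the fraction moves by it only if responder status flips. The documents do not give the number of such patients. If 1, 2 or 3 were affected and every one flipped the same way, the pooled fraction would shift by 1/34 = 2.9, 2/34 = 5.9 or 3/34 = 8.8 points.

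For scale, section 10.2 gives a 95% interval of ±15 points or less at a 75% response. The normal approximation reproduces it: 1.96 × √(0.75 × 0.25 / 34) = 1.96 × 0.0743 = 0.146. Even the 3-patient worst case is smaller than that half-width.

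**Direction.** This is not determined. A baseline lowered by lingering effect makes a 25% fall harder to reach. Worsening off drug before the baseline makes it easier. The protocol gives no duration of effect for topical clobetasol.

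**The case against.** The case against giving this weight is good, and most of it stands.

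- **The gap is narrow.** Current users of every form are already barred. The patient left over must have used a non-ointment form in the mouth, stopped before assessment, done so within 6 weeks, and still have an OMRS of at least 20 with the erythema or ulceration threshold met. That limits entry of patients whose disease is still well suppressed.
- **Ointment is the form the protocol describes in use.** Sections 1.2.3.1 and 1.2.3.2 name ointment wherever they describe clobetasol in oral practice. A reader might infer from "Ointments and creams have a disadvantage of uneven and cumbersome application" that clobetasol cream is used for oral cGVHD. The sentence is a general remark about vehicles and does not say so. The only other hint is two titles in the reference list on aqueous clobetasol in other oral conditions.
- **Carry-over is not demonstrated.** The protocol gives no reason for choosing 6 weeks. It is tempting to say that such patients will rebound on placebo and then respond on re-exposure, but no section describes rebound.
- **Earlier treatment failures are a separate matter.** A reader might add that patients who failed clobetasol can enter. So can ointment failures once 6 weeks have passed; the word ointment does not cause this, and widening the rule would not stop it.
- **There is some mitigation.** Prior therapy is recorded, randomisation spreads such patients between arms on average, and section 10.2 acknowledges heterogeneity in prior treatments.

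Two things remain. Recording prior therapy does not exclude anyone, and no analysis in section 10.2 uses it. Balance between arms helps the day-14 comparison but not a pooled change from each patient's own baseline.

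**Conclusion.** The mismatch between 2.1.2.2 and 2.1.1.8 is real on the wording. A patient who recently stopped a non-ointment intra-oral clobetasol product can enter 35 to 42 days sooner after the last dose than an ointment user. Carry-over into the OMRS baseline and into the baseline cortisol, ACTH and plasma clobetasol values is possible. Its size and direction are unknown, and few patients are likely to be involved. Possible outside referral keeps that number from being safely taken as zero.

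A reader might infer that each such patient moves the response fraction by 2.9 or 5.9 points. The documents do not support that: those figures are maxima, reached only if prior exposure changes responder status. The conclusion rests on a literal reading of the criteria and on the protocol giving no reason to treat the other forms differently. It is a low-priority clarification and does not undermine the design.

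**What to change.** Reconcile 2.1.2.2 with 2.1.1.8 so that the sponsor's existing look-back covers intra-oral clobetasol in any form, and make the same change in the eligibility checklist. If the sponsor does intend other forms to be treated differently, the protocol should say so, give the reason, and state which interval applies to a patient who has already stopped. No new window and no new procedure is needed.

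The cost is a few words in one criterion and one checklist item. The downside is that an occasional patient waits longer before enrolling. If patients have already been enrolled, the prior oral therapy item in Appendix H can be used to count those with recent non-ointment clobetasol and to report the number beside the primary result.

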#### 2.2 SCREENING EVALUATION

Evaluation outlined in Section 3.3.1 and Appendix A.

#### 2.3 **REGISTRATION PROCEDURES**

Authorized staff must register an eligible candidate with NCI Central Registration Office (CRO) within 24 hours of signing consent. A registration Eligibility Checklist from the web site (http://home.ccr.cancer.gov/intra/eligibility/welcome.htm) must be completed and must be completed and sent via encrypted email to: NCI Central Registration Office (HOIS) <[contact]>. After confirmation of eligibility at Central Registration Office, CRO staff will call pharmacy to advise them of the acceptance of the patient on the protocol prior to the release of any investigational agents. Verification of Registration

will be forwarded electronically via e-mail to the research team. Voicemail is available during non-working hours.

## 2.4 RANDOMIZATION (OR STRATIFICATION) PROCEDURES:

[name] will create the randomization lists using variable block sizes. Patients will be randomized with a single stratification factor to try to ensure a balanced distribution among those getting placebo or not initially: being identified as having a high intensity of immunosuppression (2 or more agents/modalities  $\pm$  prednisone $\geq$ 0.5 mg/kg/day) vs. no or a lesser intensity of systemic immunosuppression according to the Intensity of Immunosuppression Scale.

Once patients have been evaluated and meet all eligibility requirements, patients will be registered with the NCI Central Registration Office and be randomized to either clobetasol or placebo. Change of systemic immunosuppressive regimen occurring after enrollment will not be allowed, and if this is necessary during the 2-week blinded phase of the study to control progressive systemic cGVHD, the patient will come off the study. Other medication changes will be documented at the interim or final (end of treatment) appointment and taken into consideration in the final analysis. However, given the small, pilot nature of the study, it is unlikely that the effect of all potential confounders can be meaningfully taken into account.

## **3** STUDY IMPLEMENTATION

## 3.1 STUDY DESIGN

This is a randomized, double blind, placebo-controlled, pilot study of clobetasol 0.05% topical oral rinse with an open label cross-over or extension period. Consenting subjects with clinically significant oral chronic GVHD will be randomized to clobetasol 0.05% or placebo oral rinse. The placebo will be flavored with quinine, to approximate the "bitter" taste of clobetasol.

Subjects will be evaluated at bi-weekly intervals while on the study intervention. OMRS score will serve as the primary outcome measure. At the first 2 week interim appointment patients will be unblinded and started on the clobetasol oral rinse open label. In the absence of progressive oral disease on the scheduled interim evaluations during the 4-week clobetasol treatment period, all patients will complete a total of 4 weeks of treatment with clobetasol. Therefore, patients who were originally assigned to clobetasol arm will receive additional 2 weeks of treatment, and patients assigned to placebo arm will undergo an additional 4 weeks of treatment with clobetasol after unblinding. Patients with progressive disease after 2 weeks of therapy with clobetasol will be considered non-responders, taken off-treatment and treated as appropriate in consultation with primary clinician. Within 90 days of the end of the 1 month of treatment, all patients with evidence of benefit (response or stable disease) will be given an option to continue treatment with clobetasol 0.05% with or without additional treatment as deemed clinically necessary for 1 month after the conclusion of the initial treatment period. Additional follow-up appointment will be scheduled for all patients 1 month after completion of treatment. The change in OMRS scores from baseline to 4 weeks of mouth rinse usage will be the primary outcome variable. For the placebo group, the OMRS score at the end of the blinded phase/beginning of clobetasol rinse use (day 14) will serve as the baseline for the primary outcome. Difference in OMRS score between the groups (placebo and clobetasol) at the end of the 14-day blinded phase will serve as a secondary outcome measure. The study schedule of events is outlined in Appendix G.

# 

#	Because of problems with your teeth, denture or mouth have you	Never (0)	Hardly ever (1)	Occasionally (2)	Often (3)	Very Often (4)
1	Had trouble pronouncing words					
2	Felt sense of taste has worsened					
3	Had painful aching in the mouth					
4	Found it uncomfortable to eat any foods					
5	Have been self-conscious					
6	Felt tense					
7	Had an unsatisfactory diet					
8	Had to interrupt meals					
9	Found it difficult to relax					
10	Have been a bit embarrassed					
11	Have been irritable with other people					
12	Had difficulty doing usual jobs					
13	Felt life in general was less satisfying					
14	Have been totally unable to function					

Total \_\_\_\_\_

Abbreviated Title: Clobetasol oral rinse for oral cGVHD

Version Date: January 24, 2017

# Date: /\_\_\_/\_\_\_\_ Timepoint: LIP print name: [name] LIP Signature: \_\_\_\_\_\_\_\_

#	Because of problems with your teeth, denture or mouth have you	Never (0)	Hardly ever (1)	Occasionally (2)	Often (3)	Very Often (4)
1	Had trouble pronouncing words					
2	Felt sense of taste has worsened					
3	Had painful aching in the mouth					
4	Found it uncomfortable to eat any foods					
5	Have been self-conscious					
6	Felt tense					
7	Had an unsatisfactory diet					
8	Had to interrupt meals					
9	Found it difficult to relax					
10	Have been a bit embarrassed					
11	Have been irritable with other people					
12	Had difficulty doing usual jobs					
13	Felt life in general was less satisfying					
14	Have been totally unable to function					

Total \_\_\_\_\_

Appendix G

ate: \_\_\_/\_\_/\_\_ Timepoint: \_\_\_\_\_ LIP print name: [name] ays\_LIP Signature: \_\_\_\_\_

cause of problems with your teeth, denture or mouth have you				Never (0)	Hardly ever (1)	Occasionally (2)	Often (3)
ad trouble pronouncing words							
It sense of taste has worsened							
nd painful aching in the mouth							
und it uncomfortable to eat any foods							
ave been self-conscious							
lt tense							
nd an unsatisfactory diet							
nd to interrupt meals							
und it difficult to relax							
we been a bit embarrassed							
we been irritable with other people							
d difficulty doing usual jobs							
lt life in general was less satisfying						•	
we been totally unable to function							
						-	
				I	1	1	

Т

tal

Appendix GFor pediatric patients (< 18 years of age at enrollment), ACTH stimulation test and oral biopsy will be done as clinically indicated, and are not required by the protocol. These procedures may still be done for clinical diagnostic and monitoring purposes.

